### **3.1.4 Extension**

Subjects will have the option to roll over to the extension study after they complete their Week 60 visit. In the extension study, all subjects will receive 15 mg losmapimod PO BID. Subjects who wish to roll over into the extension must complete all procedures from the Week 60 end of treatment period/start of extension visit (Table 2).

Subjects will remain in the extension until 90 days after commercial drug is available post regulatory approval or until the study is discontinued by the sponsor. All subjects who complete or discontinue from treatment will complete a safety follow-up visit 7 days (±3 days) after the last dose of study drug.

During the extension, subjects will attend clinic visits approximately every 24 weeks (Table 3). Losmapimod will be administered BID and should be taken with food.

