## 4. STUDY POPULATION

### 4.1 Population (Base)

This study will enroll approximately 16 subjects with genetically confirmed FSHD1. Eligibility will be reviewed and documented by an appropriately qualified member of the investigator's team before subjects are enrolled.

Subjects who meet all of the inclusion criteria in Section 4.2 and none of the exclusion criteria in Section 4.3 will be eligible for the study.

Enrollment has completed with 14 subjects with genetically confirmed FSHD1 included in the study.

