### **6.4 Summary of Known and Potential Risks and Benefits**

#### **6.4.1 Known and Potential Risks**

There are no known contraindications to the administration of losmapimod.

Losmapimod should not be administered to subjects who are hypersensitive to losmapimod or the excipients used in the losmapimod tablets.

Losmapimod should not be administered to pregnant women or women at risk of becoming pregnant because it was associated with embryo-foetal malformations in rats and rabbits.

Abnormal elevation of transaminases with or without increased bilirubin has been observed with other p38 $\alpha$  inhibitors. Although there is little evidence that this occurs with losmapimod based on the experience from previous clinical trials in over 3,500 subjects, monitoring for potential liver enzyme abnormalities is specified in the protocol as part of safety monitoring.

Clinical studies to date have not shown any consistent increase in the incidence, severity, or type of infections in subjects who received losmapimod compared to placebo. However, because of a potential modest impact of losmapimod on immune function due to inhibition of p38 $\alpha$  pharmacology, there could be circumstances when the theoretical risk of losmapimod administration may outweigh its potential benefits to subjects with FSHD1 (eg, concurrent administration with cytotoxic chemotherapy for cancer). Whether losmapimod could decrease the efficacy of immunisations has not been formally studied.

There has been no increase in renal insufficiency or renal adverse events with losmapimod

compared to placebo in previous clinical trials. However, a small increase in serum creatinine (ratio: 1.07; 95% CI, 1.02 to 1.11) was noted in 1 study, and similar trends were observed in other studies. This increase appears to attenuate with continued treatment and is reversible upon discontinuation. Losmapimod is an inhibitor of MATE1 renal transporter, which may explain this finding.

There has been no increase in cardiac arrhythmias or ECG abnormalities with losmapimod compared to placebo in the clinical trials.

Although no studies have been conducted to evaluate the potential of losmapimod for abuse and dependence, there is no reason to suspect that this will be the case based on its mechanism of action.

There are currently no identified adverse drug reactions and no expected safety risks of losmapimod that would prevent further clinical development in FSHD1 or any other indication.

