**Table 3 Schedule of Assessments – Extension**

Assessment	Week 72 Week 120 Week 168 etc.	Week 84 Week 132 Week 180 etc.	Week 96 Week 144 Week 192 etc.	Week 108 Week 156 Week 204 etc.	ET Visit a	End of Study Follow-Up
Visit Window (weeks) b	±4	±4	±4	±4		
Outpatient visits		X		X	X	X
Safety phone visit	X		X			
Weight/Height				X		X
Physical examination d				X		
Vital signs e		X		X	X	X
ECG f		X		X	X	X
Urine hCG test g	X h	X	X h	X	X	
Serum chemistry		X		X	X	X
Haematology		X		X	X	X
Losmapimod dispensing		X		X		
AE Monitoring	Continuous from signing the ICF through the safety follow-up visit					
Concomitant medications	Continuous from signing the ICF through the safety follow-up visit					
Concomitant treatments and procedures	Continuous from signing the ICF through the safety follow-up visit					

a. If a subject prematurely discontinues study treatment during the extension, they will be encouraged to remain in the study and continue with all other aspects of the study. If a subject decides to prematurely discontinue study treatment during the Extension and not continue with all other aspects of the study, they will be considered to have withdrawn from the study. If a subject withdraws from the study during the extension, they will be asked to complete the ET visit as soon as possible after the decision to terminate study participation and to complete the safety follow-up visit 7 (±3) days after their last dose of study drug. If the ET visit will be scheduled more than 7 days after the last dose of study drug, the safety follow-up and ET visits may be combined, with no duplication of assessments required.

b. Any visit can be split into 2 days with overnight hotel stay as needed to accommodate busy site schedules.

- d. A full physical examination, including a neurological examination, will be performed annually. Symptom-directed physical examinations and laboratory assessments can be performed at any time at the discretion of the investigator.
- e. Vital sign measurements will be performed after subjects have rested for at least 5 minutes.
- f. Standard 12-lead ECGs will be performed after the subject has been supine for at least 5 minutes. ECGs are not mandatory assessments and will be carried out at the discretion of the investigator.

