### 2.3.2 Study Day

Study Day will be calculated from the reference start date and will be used to show start/stop day of assessments and events. Reference start date (Day 1) is defined as the first day of treatment. Study Day = date of event – reference start date + 1. In the situation where the event date is partial or missing, Study Day, and any corresponding durations will appear partial or missing in the listings.

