### 2.3.5 Analysis Visit Windows

The following non-overlapping visit windows will be used to assign data to visits for data analyses:

Table 1 Visit windows for measurements

Adjusted Defined Windows Visit	Scheduled Study Day	Maximum Windows
Baseline Visit (First dose/Day 1)	Day 1	<= Day 1
Week 4 post-treatment	Day 28	>Day 1 to <=Day 42
Week 8 post-treatment	Day 56	>Day 42 to <=Day 98
Week 20 post-treatment	Day 140	>Day 98 to <=Day 182
Week 32 post-treatment	Day 224	>Day 182 to <=Day 266
Week 44 post-treatment	Day 308	>Day 266 to <=Day 350
Week 56 post-treatment	Day 392	>Day 350 to <=Day 406
60 Weeks post-treatment (EOS, Protocol Visit 10)	Day 420	>Day 406
64 Weeks post-treatment (Protocol Week 72)	Day 448	>Day 406 to <=490

Adjusted Defined Windows Visit	Scheduled Study Day	Maximum Windows
76 Weeks post-treatment (Protocol Week 84)	Day 532	>Day 490 to <=Day 574
88 Weeks post-treatment (Protocol Week 96)	Day 616	>Day 574 to <=Day 658
100 Weeks post-treatment (Protocol Week 108)	Day 700	>Day 658 to <=Day 742
112 Weeks post-treatment (Protocol Week 120)	Day 784	>Day 742 to <=Day 826
124 Weeks post-treatment (Protocol Week 132)	Day 868	>Day 826 to <=Day 952
148 Weeks post-treatment (Protocol Week 156)	Day 1036	>Day 952 to <=Day 1120
172 Weeks post-treatment (Protocol Week 180)	Day 1204	>Day 1120 to <=Day 1288
196 Weeks post-treatment (Protocol Week 204)	Day 1372	>Day 1288 to <=Day 1456
220 Weeks post-treatment (Protocol Week 228)	Day 1540	>Day 1456 to <=Day 1624
244 Weeks post-treatment (Protocol Week 252)	Day 1708	>Day 1624 to <=Day 1792
268 Weeks post-treatment (Protocol Week 276)	Day 1876	>Day 1792 to <=Day 1960

Only subjects terminating the study after Week 56 post-treatment will have the Week 60 follow-up (EOS) visit. Subjects proceeding to the extension will continue to 64 Weeks post-treatment (protocol week 72) visit. Subjects will remain in the extension until 90 days after commercial drug is available post regulatory approval or until the study is discontinued by the sponsor. During the extension, subjects will attend clinic visits approximately every 24 weeks. All subjects who complete or discontinue from treatment will complete a safety follow-up visit 7 days ( $\pm 3$  days) after the last dose of study drug.

If multiple visits are recorded in the same analysis window, the later visit will be used in the analysis.

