## 2.4 MULTIPLE COMPARISONS/MULTIPLICITY

No formal statistical tests will be employed in the study, therefore there is no multiplicity adjustment for type I error to be made.

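### SAP 2.3.5 lets extension safety follow-up values, taken 4 to 10 days off drug, enter treatment-week rows and in some cases replace the on-drug value

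*SAP*

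**What the plan says.** **Assignment.** SAP 2.3.5 states: "The following non-overlapping visit windows will be used to assign data to visits for data analyses". Windows are in study days, and SAP 2.3.2 sets the origin: "Reference start date (Day 1) is defined as the first day of treatment". The tie rule is "If multiple visits are recorded in the same analysis window, the later visit will be used in the analysis". Neither the windows nor the tie rule refers to treatment status.

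**Follow-up visit.** Protocol 3.1.4 says "All subjects who complete or discontinue from treatment will complete a safety follow-up visit 7 days" (±3 days) after the last dose, and SAP 2.3.5 repeats this. Footnote a of Protocol Table 3 asks subjects who withdraw during the extension to "complete the safety follow-up visit 7 (±3) days after their last dose of study drug". Table 3 gives the visit its own column, with vital signs, ECG, serum chemistry and haematology. Footnote f makes extension ECGs discretionary.

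**Rows.** SAP Table 1 has 12 extension rows, from protocol Week 72 to Week 276. Its only follow-up row is labelled for Protocol Visit 10, with scheduled Day 420 and a window of everything after Day 406. The text below the table ties that row to subjects who leave at the end of the main study.

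**Use.** Laboratory and vital-sign values and changes are summarised by visit, with by-visit shift tables (SAP 3.2.3, 3.2.4.1). ECG interpretation shifts are also by visit (SAP 3.2.4.3). With AEs, these make up the extension's primary endpoint (SAP 1.4.1). SAP 2.3.3 limits end of treatment to visits while on treatment.

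**The concern.** A value taken 4 to 10 days after the last dose is not an on-treatment measurement, yet the windows give it nowhere to go but a treatment-week row. If an on-drug visit lies in the same window, the later-visit rule drops the on-drug value and keeps the off-drug one. If none does, the off-drug value becomes that week's only value for the subject.

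This matters where an effect fades off drug. Protocol 6.4.1 reports a small serum creatinine rise in one earlier study (ratio 1.07, 95% CI 1.02 to 1.11) and adds: "This increase appears to attenuate with continued treatment and is reversible upon discontinuation". Subjects who stop for a safety reason are among those whose last on-drug value could drop out of the by-visit tables. Late extension rows may also hold few subjects, so a few such values could carry weight.

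**Working it through.** **1. Reproduce the scheduled days.** Dosing starts at Visit 4, nominal protocol Week 8 (Protocol Table 2, footnote c), so study day = (protocol week − 8) × 7. Week 72 gives 64 × 7 = 448, Week 84 gives 76 × 7 = 532, and Week 276 gives 268 × 7 = 1876. All 12 extension rows match SAP Table 1.

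**2. Last dose on the day of an in-window clinic visit.** Inputs: the clinic visit is on the scheduled day ± 28 days (the ±4-week window in Table 3), and the follow-up is 4 to 10 days later. That is 57 × 7 = 399 date combinations per row.

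| Protocol week | Table 1 window (days) | Earliest clinic day | Latest follow-up (scheduled + 38) | Upper limit |
|---|---|---|---|---|
| 84 | 491–574 | 504 | 570 | 574 |
| 108 | 659–742 | 672 | 738 | 742 |
| 132 | 827–952 | 840 | 906 | 952 |
| 156 | 953–1120 | 1008 | 1074 | 1120 |

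The remaining clinic rows (Weeks 180, 204, 228, 252 and 276) have the same spacing as Week 156: the latest follow-up is 38 days after the scheduled day and the limit is 84 days after. In all nine rows, 399 of 399 combinations stay in one window.

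This takes the SAP's scheduled day as the anchor. If visits are counted from Visit 2 and Visit 4 was a week early, days shift by 7. The latest follow-up is then Day 577 against 574 (Week 84) and Day 745 against 742 (Week 108). In each of those two rows 3 + 2 + 1 = 6 combinations cross, leaving 393 of 399. Later rows are unaffected (for example 913 against 952).

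**3. Last dose on another day.** The documents give no distribution of stopping days, so these are assumptions.
- On-drug early termination (ET) visit on a random day of a W-day window, with a 7-day gap: both visits share the window with probability 1 − 7/W. This is 92% for the 84-day windows, 94% for the 126-day window (protocol Week 132) and 96% for the 168-day windows.
- No ET visit, last dose uniform over a 168-day window, clinic visit at mid-window on average: an on-drug value is replaced in (84 − 7)/168 = 46% of cases. In the other 54% the follow-up is the only value in its row.
- ET visit combined with the follow-up (footnote a allows this when the ET visit is more than 7 days after the last dose): that pair needs no tie-break, but the single visit is still off drug.

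**4. Can the EOS row take the visit?** Its window is everything after Day 406, so it overlaps all 12 extension windows although the windows are called non-overlapping. Nor does it catch its own visit by day. Protocol 3.1.3 puts Visit 10 at Week 64 ± 2 weeks, which is (64 − 8) × 7 = Day 392, range 378 to 406. All 29 days fall in the Week 56 window (351 to 406).

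**5. Which outputs are exposed.**
- Exposed: by-visit means, changes from baseline and by-visit shift tables for laboratory tests, vital signs and any ECG.
- Not exposed: end-of-treatment summaries (SAP 2.3.3), shift tables using the highest and lowest treatment-period value (SAP 3.2.3, 3.2.4.1), QTc outlier counts (SAP 3.2.4.3), date-based TEAE tables (SAP 3.2.2) and listings.

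**6. Illustration of size.** Assume an on-drug creatinine ratio of 1.07 and full reversal by the follow-up. With k of n values off drug, the row's geometric mean ratio is 1.07^(1 − k/n). For n = 14 and k = 1, 3, 5 this is 1.0648, 1.0546, 1.0445. For n = 5 and k = 3 it is 1.0274. Neither assumption is established by the documents.

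**The case against.** - **Other analyses protect the safety reading.** This largely stands. An extreme last on-drug laboratory or vital-sign value still reaches the highest/lowest shift tables and the listings, and the end-of-treatment summaries use on-treatment visits. None of these corrects a by-visit mean or shift cell. SAP 2.3.3 also shows that the authors thought on-treatment status mattered, but the by-visit rule omits it.
- **The open-ended EOS row may be meant for this visit.** SAP 2.3.4 defines end of study as the last completed visit, and Table 3 calls the visit an end-of-study follow-up. The Day 420 and Visit 10 labels, the restriction to subjects not entering the extension, and the overlap with every extension row all count against this. At best the assignment is undefined.
- **The SAP counts AEs as treatment-emergent up to 7 days after stopping.** That is an event-date rule and does not make a laboratory value on-treatment. It does show that a cut at the last dose is one convention among several.
- **Creatinine is weak evidence.** This stands. The same protocol sentence says the rise attenuates with continued treatment, and extension subjects have already had about a year of drug. The protocol does not say how fast the rise reverses.
- **The study is small and descriptive.** "No formal statistical tests will be employed in the study", and "Enrollment has completed with 14 subjects with genetically confirmed FSHD1 included in the study". This limits the consequence, but by-visit descriptive tables are then a main form in which these data are reported.

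**Conclusion.** The point holds in a limited form. Applied literally, SAP 2.3.5 places off-drug follow-up values in treatment-week rows. Replacement of an on-drug value is certain when the last dose is on an in-window clinic day, taking the SAP's scheduled days as the anchor. Otherwise it depends on whether an on-drug visit shares the window. The follow-up visit affects at most one window per subject. Fourteen subjects is a ceiling, because the number entering the extension is not stated.

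A reader might infer that the on-drug value is lost in every subject's final window, or that a safety signal would disappear. The documents do not support either. Replacement needs an on-drug visit in the same window, and the unexposed outputs in step 5 still carry the on-drug values. Nor can one say that the last rows would be mostly off drug: that would need a common stopping date, which is not known. The size of any distortion is unknown, and 1.07 serves only as an illustration.

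**What to change.** In SAP 2.3.5:

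1. Limit treatment-week rows to on-treatment assessments, for example those dated on or before the last dose, and apply the later-visit rule only among those.
2. Add a row 'Safety follow-up (off treatment)', defined by the last-dose date, which also takes any ET visit held after the last dose. Show it beside the last on-treatment value.
3. Limit the EOS row to main-study Visit 10, assigned by visit rather than by day, because step 4 shows that the day rule does not reach it.

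If the team prefers a 7-day allowance to match the TEAE rule, the follow-up still needs its own row, because 4 to 10 days lies on both sides of that limit.

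The cost is an on-treatment flag and a few lines of text, with no new data. The downside is slightly smaller n in some late rows. The off-drug values stay in the report under their own label, where any reversal can be seen.

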### 2.3.6 Missing Data Handling Rules

#### ADVERSE EVENTS

Partial AE onset dates will be imputed as follows:

1. If the onset date of an adverse event is missing day only, it will be set to:

- a. First day of the month that the AE occurred, if month/year of the onset of AE is different from month/year of medication.
  - b. The day of treatment if the month/year of the onset of AE is the same as month/year of treatment and month/year of AE resolution date is different.
  - c. The day of treatment or day of AE resolution date, whichever is earlier, if month/year of the onset of AE and month/year of treatment and month/year of the AE resolution data are same.
2. If the onset data of an adverse event is missing both day and month, it will be set to the earlier of:
  - a. January 1 of the year of onset, as long as this date is after the date of treatment.
  - b. Month and day of treatment if the date is the same year that the AE occurred.
  - c. The AE resolution date.
3. Completely missing AE onset dates will not be imputed.

Partial AE resolution dates not marked as ongoing will be imputed as follows:

1. If the resolution date of an AE is missing day only, it will be set to the earliest of the last day of the month of occurrence of resolution or the day of the date of death, if the death occurred in that month
2. If the resolution date of an AE is missing both day and month, it will be set to the earliest of December 31 of the year or the day and month of the date of death, if the death occurred in that year
3. Completely missing resolution dates will not be imputed.

Missing or partial time will not be imputed.

If the severity is missing for an AE, then it is considered as unknown. If relationship of AEs to the study medication could not be derived (i.e., missing or unknown), it will be considered as related, for analysis purpose.

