### 3.2.2 Adverse Events (AEs)

The AE verbatim descriptions (investigator terms from the case report forms [CRF]) will be classified into medical terminology using the Medical Dictionary for Regulatory Activities (MedDRA). AEs will be coded to primary System Organ Class (SOC) and preferred term (PT) using MedDRA, version 23.0.

A TEAE is defined as an AE that meets any of the following conditions:

- begins on or after the first dose of study drug and before the stop of study drug + 7 days;
- begins before the first dose of study drug and worsens on or after the first dose of study drug and before the stop of study drug + 7 days;
- is completely missing an onset date and an end date;

- is completely missing an onset date and the end date is on or after the first dose of study drug.

Only those AEs that are treatment emergent will be included in summary tables. All AEs, treatment emergent or otherwise, will be presented in subject data listings.

In summary tables, the incidence of TEAEs will be reported as the number of subjects and their percentages with TEAEs within SOC and PT. Subjects will be counted only once within a SOC and PT, even if the subject experienced more than one TEAE within a specific SOC and PT. The number of subjects and their percentages with TEAEs will also be summarized by maximum severity (mild, moderate, or severe) (or by highest common terminology criteria for AEs [CTCAE] grade).

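### The rule for year-only AE onset dates has no branch for an onset year before first dose, so an event that resolves on treatment is dated at its resolution and counted as treatment-emergent

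*SAP*

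**What the plan says.** SAP 2.3.6, under the adverse event rules, treats partial onset dates in two tiers.

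- **Day missing only.** If the onset month is not the treatment month, onset is set to "First day of the month that the AE occurred, if month/year of the onset of AE is different from month/year of medication".
- **Day and month missing.** The rule takes the earliest of three candidates. Candidate (a) is "January 1 of the year of onset, as long as this date is after the date of treatment". Candidate (b) is the treatment date, available only when treatment began in the onset year. Candidate (c) is the date on which the event resolved, and it carries no condition.

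SAP 3.2.2 then defines a TEAE by onset date. An event qualifies if it "begins on or after the first dose of study drug and before the stop of study drug + 7 days". An event with an earlier onset qualifies only if it "begins before the first dose of study drug and worsens on or after the first dose of study drug", within the same upper limit. The flag decides what is tabulated: "Only those AEs that are treatment emergent will be included in summary tables".

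The schedule in Protocol Table 2 collects AEs from signing of the consent form, while dosing starts at Visit 4. The database will therefore hold AEs that began before first dose.

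**The concern.** Candidates (a) and (b) both require the onset year to be the treatment year or later. For an earlier onset year neither is available, and the unconditional candidate (c) is all that is left. An event whose recorded year places its start before dosing can therefore be given an onset during treatment.

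This differs from ordinary conservative imputation, which assigns an event to treatment when its timing relative to first dose is unknown. Here the recorded year already settles the timing, and the imputed date overrides it. The rule also bypasses the worsening condition in SAP 3.2.2. It disagrees with the day-missing rule as well, under which a pre-treatment month stays pre-treatment, so losing the month can reverse the classification.

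Safety and tolerability is the primary endpoint, and the TEAE tables are its main summary.

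**Working it through.** The plan gives no figure to reproduce, so the check is a trace of the rule.

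**Inputs**

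- Candidates (a), (b), (c) and the partial resolution-date rule: SAP 2.3.6.
- TEAE window: SAP 3.2.2. The treatment date is read as the date of first dose, as in SAP 2.3.2.
- 14 subjects enrolled: Protocol 4.1. All are assumed to have been dosed.
- Screening from Day -28 to Day -1, and first dose at Visit 4, Week 8 ± 1 week: Protocol Table 2.
- Assumed for illustration, since the documents give no dosing dates: first dose 3 February 2020 and 52 weeks (364 days) of treatment. Stop is then 1 February 2021, and stop + 7 days is 8 February 2021.

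**Step 1: which candidates survive.** Let Y be the onset year and T the first-dose date, with Y earlier than the year of T.

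- (a) needs 1 January of Y to be after T. It is always before T, so (a) fails.
- (b) needs the year of T to equal Y. It does not, so (b) fails.
- (c) remains: onset = resolution date.

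**Step 2: examples with onset recorded only as 2019**

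| Resolution | Imputed onset | TEAE by onset date? |
|---|---|---|
| 10 January 2020 | 10 January 2020 | No |
| 3 February 2020 (dose day) | 3 February 2020 | Yes |
| 15 June 2020 | 15 June 2020 | Yes |
| Year only, 2020 (imputed 31 December 2020) | 31 December 2020 | Yes |
| 3 March 2021 (stop + 30 days) | 3 March 2021 | No |
| Ongoing | None | Not determined by the rule |

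In every row with a date, the imputed onset falls outside 2019. In the three rows marked Yes, the classification is wrong as well unless the event worsened on treatment. In the last row no candidate exists. Because the year is known, the onset is not completely missing, so the missing-onset provisions of SAP 3.2.2 do not apply either.

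**Step 3: contrast with a missing day only.** Onset December 2019 with resolution on 15 June 2020 gives 1 December 2019, which is not a TEAE.

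**Step 4: sweep.** Every first-dose date in 2020 was paired with resolution dates from 60 days before to 360 days after first dose, in 5-day steps, leaving out resolutions before 31 December 2019. Onset year was fixed at the year before first dose. All 30,732 combinations fell to (c). The 26,718 with resolution on or after first dose received an onset on or after first dose, and the 4,014 with earlier resolution stayed pre-treatment (26,718 + 4,014 = 30,732). These are counts on a grid of hypothetical dates and are not probabilities.

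**Step 5: can it occur here?** The shortest scheduled interval from consent to first dose is about 7 weeks (screening just before Day 1, then Week 8 - 1). The longest is 4 + 8 + 1 = 13 weeks. If consent dates were spread evenly over the year, the share of subjects whose interval crosses a year end would be 49/365 = 13% at 7 weeks, 84/365 = 23% at 12 weeks and 91/365 = 25% at 13 weeks.

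**Step 6: size per affected subject.** 1/14 = 7.1 percentage points in a preferred term. SAP 3.2.2 counts a subject once per term, so the increment is 0 if that subject already has another TEAE in the term.

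**The case against.** The strongest reply is that the case hardly arises. Protocol 9.2.1 defines AEs as events during the study, and earlier conditions belong in medical history. An affected event must start between consent and 31 December, be recorded with a year but no month although pre-treatment visits are about 4 weeks apart, persist to first dose, and then resolve within the TEAE window. In 14 subjects the expected number is close to zero. A missing day alone is the realistic defect, and the plan handles that correctly.

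The consequence is also limited. All AEs are listed whether or not treatment-emergent, and SAP 2.3.2 leaves Study Day and durations partial or missing in listings when a date is partial, so a reader can see that the onset was incomplete. There is no formal testing. For the events at issue the error adds TEAEs and does not remove them.

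All of this stands, and it sets the rating. It does not rescue the rule, which still produces a date that its own input rules out.

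Three stronger readings are tempting, and the documents support none of them:

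- A reader might infer that every event from a prior year becomes a TEAE. It does not if it resolved before first dose, or at or beyond stop of drug + 7 days. If it is ongoing, no onset is imputed.
- A reader might take 23% as a misclassification rate. It is only the share of start dates whose 12-week interval crosses a year end, under an assumed even spread. The documents give no frequency for the other conditions.
- A reader might infer that the rule could hide a safety signal. For these events it only over-counts.

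**Conclusion.** The rule is wrong as written for one narrow case: onset known only by a year earlier than that of first dose, with resolution on or after first dose and before stop of drug + 7 days. There the imputed onset contradicts the recorded year, and the event enters the TEAE tables without having to meet the worsening condition. For an ongoing event from a prior year there is a smaller gap, since no onset date is assigned.

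The effect is at most 7.1 percentage points in a preferred term for each affected subject, and nil where that subject already has a TEAE in the term. This assumes a denominator of 14. Such events should be very rare. That is a judgement, because the documents report neither dosing dates nor the number of year-only onsets. This is a minor correction and does not threaten the safety conclusions.

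**What to change.** Add a branch to the day-and-month-missing rule in SAP 2.3.6: if the onset year is earlier than the year of first dose, impute the earlier of 31 December of the onset year and the AE resolution date, or 31 December if the event is ongoing. Classify the event as treatment-emergent only if it worsened on or after first dose, as SAP 3.2.2 already requires.

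The cap at resolution is needed. With onset year 2019, resolution on 10 November 2019 and first dose in January 2020, a bare 31 December rule would place onset after resolution; the capped rule gives 10 November 2019. In the illustration above, resolution on 15 June 2020 gives an onset of 31 December 2019, which is not a TEAE unless the event worsened. The ongoing case also receives a date.

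The cost is one sentence and about one line of code. Protocol 10.1 allows the SAP to be updated at any time during the study, with the update described and justified in the CSR. If the tables have already been run, it is enough to search the AE data for year-only onsets earlier than the year of first dose and correct any that are found.
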